## 5.2. Number of Participants

Approximately 486 participants will be randomized such that approximately 388 evaluable participants complete the double-blind treatment phase. China, Russia, and India intend to participate in the study.

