## 10. Statistical Considerations

### 10.1. Sample Size Determination

Approximately 486 patients will be randomized in a 1:1 ratio to the galcanezumab 120-mg/month or placebo treatment groups. With 243 patients per treatment group, this study will have approximately 90% power to detect an effect size of 0.33 between galcanezumab 120-mg/month and placebo treatment groups. Within the framework of a MMRM, the sample size is determined using a between-treatment group t-test, 2-sided with a type I error of 0.05, assuming a discontinuation rate of 20% during the double-blind phase. Parameters used in the sample size calculations are based on results from 2 double-blind, placebo-controlled Phase 3 studies (Studies CGAG and CGAH) and clinical justification.

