5.2. Determination of Sample Size

Approximately 486 patients will be randomized in a 1:1 ratio to the galcanezumab 120-mg/month or placebo treatment groups. With 243 patients per treatment group, this study will have approximately 90% power to detect an effect size of 0.33 between galcanezumab 120-mg/month and placebo treatment groups. Within the framework of a mixed model repeated measures (MMRM), the sample size is determined using a between-treatment group t-test, 2-sided with a type I error of 0.05, assuming a discontinuation rate of 20% during the double-blind

phase. Parameters used in the sample size calculations are based on results from 2 double-blind, placebo-controlled Phase 3 studies (CGAG and CGAH) and clinical justification.

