6.1. General Considerations

Unless otherwise specified, efficacy analyses will be conducted on an intent-to-treat (ITT) population, which will include all patients who are randomized and received at least 1 dose of study drug. Patients in the ITT population will be analyzed according to the treatment group to which they are randomized. Safety analyses will be conducted on safety population, which is the same as the ITT population. Patients in the safety population will be analyzed according to the actual treatment the patient received.

There are 5 analysis populations defined:

Intent-to-treat (ITT) population: All patients who are randomized and receive at least 1 dose of study drug.

Safety population: This population is the same as the ITT population defined above.

Open-label treatment population: All patients who enter the open-label treatment phase as indicated by receiving any injections starting from Visit 7. Patients in the open-label treatment population will be analyzed as a single group as they start with the same treatment in the study period. Analyses for open-label phase only will be based on the open-label treatment population.

Post-treatment population: All patients who enter the post-treatment phase (Study Period V) as indicated by entering any post-treatment visit (telephone or office visit). Analyses for post-treatment phase only (that is, excluding earlier study periods) will be based on post-treatment population.

GMB-treated population: All patients who have exposure to galcanezumab (GMB). The GMB-treated population will be used for summaries for GMB-treated time.

GMB-treated time is the period during which a patient received GMB.

- For patients who receive GMB in the double-blind treatment period (SP III) only, GMB-treated time begins and ends in SP III.
- For patients who receive GMB in both treatment periods, GMB-treated time begins in SP III and extends through SP IV.
- For patients who receive placebo in the double-blind treatment period, GMB-treated time begins in SP IV.

Treatment effects will be evaluated based on an overall 2-sided significance level of 0.05 for all efficacy and safety analyses. The 95% confidence intervals (CIs) for the difference in least-square means (LSMeans) between treatment groups will be provided.

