Post-treatment-emergent changes in temperature and weight	Post-treatment population with a baseline and at least 1 postbaseline observation	Low: Min of Visits 1–10 High: Max of Visits 1–10	Low: Min of Visits 10.01–12 High: Max of Visits 10.01–12
Post-treatment-emergent changes in blood pressures, pulse, and ECGs	Post-treatment population with a baseline and at least 1 postbaseline observation	Low: Last of Visits 1–10 High: Last of Visits 1–10	Low: Min of Visits 10.01–12 High: Max of Visits 10.01–12
Continuous safety analyses – change from baseline to LOCF endpoint (ANCOVA)	Post-treatment population with a baseline and at least 1 postbaseline observation	Last of Visits 1–10	Last of Visits 10.01–12
Study Periods III / IV / V Combined			
Efficacy/Health outcome analyses	ITT population with a baseline and at least 1 postbaseline observation	Visit 3	All scheduled visits $3 < \text{Visits} \leq 12$
Continuous safety analyses (repeated measures)	Safety population with a baseline and at least 1 postbaseline observation	Last of Visits 1–3	All scheduled visits $3 < \text{Visits} \leq 12$
Treatment-emergent immunogenicity	Safety population - GMB-treated patients with a baseline and at least 1 postbaseline observation	Visit 3	All Visits 3.01–12

Patient Population with Baseline and Postbaseline Definitions by Study Period and Type of Analysis

Study Period/Analysis	Patient Population	Baseline Observation	Postbaseline Observation(s)
GMB-Treated Time			
Treatment-emergent adverse events	GMB-treated population	All Visits 1–3 before double-blind phase dosing for patients treated with GMB during SP III; All Visits 1–7 before open-label phase dosing for patients treated with placebo during SP III*a	All visits after first dosing of GMB through Visit 10
Serious adverse events, discontinuations due to adverse events	GMB-treated population	NA	All visits after first dosing of GMB through Visit 10
Treatment-emergent abnormal laboratory values	GMB-treated population with normal (with respect to direction being analyzed) laboratory values at all non-missing baseline visits and who have at least 1 postbaseline observation	Visits 1–3 before double-blind phase dosing for patients treated with GMB during SP III; Visits 1–7 before open-label phase dosing for patients treated with placebo during SP III	All visits after first dosing of GMB through Visit 10: Visits 3.01–10 for GMB-treated patients during SP III; Visits 7.01–10 for placebo-treated patients during SP III

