6.14.2. Adverse Events

Treatment-emergent adverse events are defined as the reported AEs that first occurred or worsened during the post-baseline phase compared with baseline phase. For each TEAE, the severity level of the event (mild, moderate, or severe) will be determined by patient or physician opinion. The Medical Dictionary for Regulatory Activities (MedDRA) Lowest Level Term will be used in the treatment-emergent computation. For each Lowest Level Term, the maximum severity at baseline will be used as the baseline severity. If the maximum severity during post-baseline is greater than the maximum baseline severity, the event is considered to be treatment-emergent for the specific post-baseline period.

Unless specified otherwise, adverse events will be summarized as follows:

- Treatment-emergent adverse events (TEAEs)

- By preferred term (PT)
- By PT nested within system organ class (SOC)
- By maximum severity
- By considered to be related to study treatment by investigator
- Serious adverse events (SAEs) by PT
- AEs leading to treatment discontinuation by PT

For each patient and TEAE, the maximum severity for the MedDRA level being displayed is the maximum post-baseline severity observed from all associated Lowest Level Terms mapping to the MedDRA level.

For events that are gender specific, the denominator and computation of the percentage will include only patients from the given gender.

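### Galcanezumab-treated-time safety percentages mix up to 6 months of follow-up with up to 3, so they are neither a 3-month nor a 6-month risk; show them by original arm and add a rate per patient-year

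*SAP*

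**What the plan says.** SAP 6.1 defines the GMB-treated population as all patients with any galcanezumab exposure and uses it for summaries of galcanezumab-treated time. For patients randomized to galcanezumab, that time starts in the double-blind phase (SP III) and runs through the open-label phase (SP IV) if they continue. For the others, "For patients who receive placebo in the double-blind treatment period, GMB-treated time begins in SP IV".

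SAP Table CGAX. 6.1 gives one window for treatment-emergent adverse events, serious adverse events and discontinuations due to adverse events: "All visits after first dosing of GMB through Visit 10". Labs, vital signs, weight and ECG follow the same scheme.

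SAP 6.14.2 to 6.14.5 summarize by preferred term (for example "AEs leading to treatment discontinuation by PT"), by number and percentage of patients, or by incidence at any time. No person-time rate or time-to-event estimate is planned. For galcanezumab-treated time, SAP 6.14.1 plans only the distribution of 1 to 6 doses. It defines exposure in days for SP III and SP IV separately.

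**The concern.** A percentage headed galcanezumab-treated time will naturally be read as the risk on the drug. Here its value also depends on how many patients in each arm enter the open-label phase and how many drop out.

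No other planned adverse-event incidence summary covers the full 6-month course. SP III gives 3 months. The open-label population is analyzed as one group, which mixes months 4-6 of continuing patients with months 1-3 of switchers.

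The number of scheduled looks differs as well as the follow-up time, which affects any measure counted as ever abnormal.

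**Working it through.** **Group sizes.** The documents state no event rate for galcanezumab-treated time, so the planning figures serve only to size the groups. "With 243 patients per treatment group, this study will have approximately 90% power to detect an effect size of 0.33", "assuming a discontinuation rate of 20% during the double-blind phase": the standard two-mean formula gives 193 per arm, or 193/0.8 = 242 after rounding up, against the plan's 243. Power with 194 completers per arm is 0.90. Completers: 486 × 0.8 = 388.8, in line with "approximately 388 evaluable participants complete the double-blind treatment phase". Per arm, N = 243 and C = 0.8 × 243 = 194.4.

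**Scheduled looks after first galcanezumab dose** (Schedule of Activities, through Visit 10):

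| Measure | Original galcanezumab arm | Switchers |
|---|---|---|
| Labs, ECG, weight | 2 (Visits 7, 10) | 1 (Visit 10) |
| Vital signs | 6 (Visits 5-10) | 3 (Visits 8-10) |
| Adverse-event contacts | 7 (Visits 4-10) | 3 (Visits 8-10) |

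The sustained-elevation criteria need two consecutive visits: 5 scheduled pairs against 2.

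**Assumptions not in the documents:** 80-100% of completers in each arm enter SP IV (O = 155.52 to 194.4); no SP IV dropout; SP III dropouts average 1.5 months on drug; constant hazard; three-month risk p3 = 10%.

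Monthly hazard h = -ln(1 - 0.10)/3 = 0.0351. Risk over 1.5 months = 1 - e^(-1.5h) = 5.13%; over 3 months, 10.0%; over 6 months, 1 - 0.9² = 19.0%.

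Expected patients with an event:
- Original arm: 0.2N × 5.13% + (C - O) × 10% + O × 19%
- Switchers: O × 10%

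| SP IV entry | Original arm | Switchers | Pooled |
|---|---|---|---|
| 100% | (2.49 + 0 + 36.94)/243 = 16.2% | 19.44/194.4 = 10.0% | 58.87/437.4 = 13.5% |
| 80% | (2.49 + 3.89 + 29.55)/243 = 14.8% | 15.55/155.52 = 10.0% | 51.48/398.52 = 12.9% |

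The same formula at p3 = 5% gives 6.6-6.8% pooled against 9.8%. Switchers are 39-44% of the pooled patients but 29-32% of the patient-time.

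**Source of the shortfall from 19.0%:**
- 100% entry: total 5.5 points, of which 2.8 are already present in the original arm alone. Switchers account for about 50%.
- 80% entry: total 6.1 points, of which 4.2 are already present in the original arm. Switchers account for about 31%.

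With no dropout and full entry the pooled figure would be (19.0 + 10.0)/2 = 14.5%, and the whole shortfall would come from switchers.

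**Other hazards.**
- Hazard halves after month 3: the 6-month risk is 1 - 0.9 × √0.9 = 14.6% and the pooled figure is 11.2-11.5%, a ratio of about 0.77-0.79.
- No events after month 3: the original arm gives 0.2 × 5.13% + 0.8 × 10% = 9.0%, switchers 10.0%, and the pooled figure at full entry is 9.5% against a true 10.0%. That small gap comes from dropout; adding switchers raises the figure.

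**The case against.** The SAP does not say that galcanezumab-treated time will be shown in one column. It says so for the open-label population but not here; the safety-topic summaries in 6.14.2.1 are by treatment group; and Table CGAX. 6.1 sets windows by original arm. This stands in part: a single pooled column is the natural reading, not an explicit statement.

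The summary is also descriptive. The safety objective against placebo is met by SP III, where planned follow-up is equal. The dose distribution shows the exposure mix, injection-site events are also summarized by timing, and continuous safety measures are modeled through Visit 10. This limits the importance of the point but does not supply an interpretable adverse-event incidence for the full course.

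A reader might infer three stronger things that the documents do not support:
- **That the percentage always understates 6-month risk.** This requires events in months 4-6, and the documents give no hazard.
- **That the whole shortfall of about 30% is due to pooling.** Under the planning assumptions, about 50-69% of it comes from dropout and non-entry in the original arm.
- **That the figure falls as more placebo patients switch, whatever the drug does.** When entry rises equally in both arms from 80% to 100%, it rises from 12.9% to 13.5%. With no events after month 3, adding switchers raises it too.

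Finally, a patient-year rate also depends on the follow-up mix if events cluster early. That is a reason to add the rate rather than replace the percentage with it.

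**Conclusion.** The point holds as a reporting weakness worth correcting. Follow-up (up to 6 months against up to 3) and scheduled looks (2 against 1 for labs, ECG and weight; 6 against 3 for vital signs) differ by original arm, and the planned percentages do not account for either. With a 10% three-month risk and the stated assumptions, the pooled figure is 12.9-13.5% against a 6-month risk of 19.0%, about 29-32% lower in relative terms; 31-50% of that gap is due to switchers. These figures rest on a constant hazard, 80-100% SP IV entry and no SP IV dropout, none of which the documents state. For events confined to the first 3 months the mixing does no such harm. The randomized SP III comparison is untouched.

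**What to change.** In SAP 6.14, for galcanezumab-treated time:
1. Present safety results by original randomized arm (up to 6 months; up to 3 months) beside any pooled column.
2. For adverse events, add to the percentages a first-event rate per 100 patient-years at risk with a 95% CI. Time at risk needs a new derivation, from first galcanezumab dose to first event or end of galcanezumab-treated time. The durations in 6.14.1 cannot be used as they stand, because they are by period and do not stop at the first event.
3. Report lab, ECG, weight and vital-sign categories by original arm, because a person-time rate does not correct for unequal numbers of looks.

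The split alone will not turn the original-arm figure into a 6-month risk, since dropout and non-entry remain; the rate addresses that part.

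The cost is SAP wording, one derived variable from dates already collected, and longer tables. The rate is easiest to interpret when the hazard is roughly constant, and a footnote should say so.

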Treatment-emergent changes in temperature and weight	GMB-treated population with a baseline and at least 1 postbaseline observation	Min/max of Visits 1–3 before double-blind phase dosing for patients treated with GMB during SP III for low/high, respectively; Min/max of Visits 1–7 before open-label phase dosing for patients treated with placebo during SP III for low/high, respectively	Min/max of all visits after first dose of GMB through Visit 10 for low/high, respectively; Visits 3.01–10 for GMB-treated patients during SP III; Visits 7.01–10 for placebo-treated patients during SP III.

Patient Population with Baseline and Postbaseline Definitions by Study Period and Type of Analysis

Study Period/Analysis	Patient Population	Baseline Observation	Postbaseline Observation(s)
GMB-Treated Time			
Treatment-emergent changes in blood pressure, pulse, and ECGs	GMB-treated population with a baseline and at least 1 postbaseline observation	Last non-missing value from Visits 1–3 before double-blind phase dosing for patients treated with GMB during SP III; Last non-missing value from Visits 1–7 before open-label phase dosing for patients treated with placebo during SP III.	Min/max of all visits after first dosing of GMB through Visit 10 for low/high, respectively: Visits 3.01–10 for GMB-treated patients during SP III; Visits 7.01–10 for placebo-treated patients during SP III.
Treatment-emergent immunogenicity	GMB-treated population with a baseline and at least 1 postbaseline observation	Visit 3	All Visits 3.01–10

Abbreviations: AE = adverse event; ANCOVA = analysis of covariance; ECG = electrocardiogram; GMB = galcanezumab; ITT = intent-to-treat; LOCF = last observation carried forward; max = maximum; min = minimum; NA = not applicable; SP = study period.

*a, AEs that occurred on the visit date of Visit 3 or Visit 7 will be determined to be predose or after dose based on AE start time and the injection time: predose if AE start time is before the injection time and post dose if AE start time is after the injection time. Note: Visit 3.01 indicates the first unscheduled visit occurring after Visit 3 and prior to Visit 4. Visit 7.01 indicates the first unscheduled visit occurring after Visit 7 and prior to Visit 8.

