6.13. Evaluation of Immunogenicity

To evaluate the changes in immunogenicity data (Anti-LY2951742 [ADA and NAb]) after treatment, the following statistical analyses are planned for comparison between treatment groups:

- The incidence of ADA positive during baseline will be summarized.
- The incidence of treatment-emergent ADA (TE ADA) between treatment groups will be summarized and compared for SP III. The incidence of TE ADA for galcanezumab-treated patients during galcanezumab treatment and the incidence of TE ADA for galcanezumab-treated patients during galcanezumab treatment and post-treatment phase combined will be summarized. This analysis will be done for each immunogenicity analyte (ADA and NAb). The baseline and postbaseline definitions for each Study Period is shown in [Table CGAX. 6.1](#). Treatment-emergent ADA will be defined as any of the following:
 - a negative baseline result and a positive postbaseline ADA result with a titer ≥ 20 . This is also called treatment-induced ADA.
 - a positive baseline result and a positive postbaseline ADA result with a ≥ 4 -fold increase in titers (for example, baseline titer of 10 increasing to ≥ 40 postbaseline). This is called treatment-boosted ADA.
- The incidence of TE ADA and NAb Positive combined between treatment groups will be summarized for the same time periods as planned for the incidence of TE ADA.

The following will also be provided:

- Listing of subjects with TE ADA at any time during study, NAb Status will also be displayed.

- Listing of subjects with TE hypersensitivity reactions or TEAEs related to injection sites for subjects with ADA present at any time.

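### ADA that appears on placebo is counted as emergent on galcanezumab for patients who switch at Visit 7

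*SAP*

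**What the plan says.** SAP Section 6.13 plans three summaries of treatment-emergent ADA: a between-group comparison in Study Period III, a summary on galcanezumab, and a summary on galcanezumab plus the post-treatment phase. It describes the second as "The incidence of TE ADA for galcanezumab-treated patients during galcanezumab treatment" and takes the baseline and post-baseline definitions from Table CGAX.6.1.

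In the galcanezumab-treated-time block of that table, the immunogenicity row applies to the "GMB-treated population with a baseline and at least 1 postbaseline observation". Its baseline is Visit 3 and its post-baseline window is "All Visits 3.01–10", with no distinction by double-blind treatment. The corresponding row for Study Periods III, IV and V combined covers the "Safety population - GMB-treated patients with a baseline and at least 1 postbaseline observation", with baseline Visit 3 and a window from 3.01 to 12.

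SAP Section 6.1 defines the galcanezumab-treated population by any exposure to the drug. It adds: "For patients who receive placebo in the double-blind treatment period, GMB-treated time begins in SP IV".

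**The concern.** A placebo patient who enters the open-label phase belongs to the galcanezumab-treated population but receives no galcanezumab before Visit 7. The window in the immunogenicity row opens three months before that first dose. Antibodies that appear on placebo therefore enter a figure labelled as incidence during galcanezumab treatment, and the cell contradicts the SAP's own definition of galcanezumab-treated time.

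Immunogenicity is a stated secondary objective, and this incidence will be read as a property of the drug. The rule also affects two other things:

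- **Denominator.** A placebo-period sample satisfies the requirement for at least one post-baseline observation, so a switcher with no sample after galcanezumab can still be counted.
- **Boosted ADA.** A 4-fold rise is judged against Visit 3 and not against the pre-dose Visit 7 sample, which is the natural baseline for a switcher.

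**Working it through.** The plan states no figure to reproduce here, so the check compares the texts and then illustrates the size.

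**1. Samples inside the window.** The protocol's Schedule of Activities places immunogenicity samples at Visits 3, 5, 7, 10 and 12. Footnote h requires them before dosing at dosing visits. Visits 3.01 to 10 therefore contain scheduled samples at Visits 5, 7 and 10. For a switcher, two of these three precede any galcanezumab.

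**2. Comparison with the other rows of the same block.**

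| Row | Baseline, placebo in Period III | Post-baseline, placebo in Period III |
|---|---|---|
| Adverse events | Visits 1–7, before open-label dosing | after first galcanezumab dose |
| Serious events, discontinuations | not applicable | after first galcanezumab dose |
| Laboratory | Visits 1–7, before open-label dosing | 7.01–10 |
| Temperature, weight | Visits 1–7, before open-label dosing | 7.01–10 |
| Blood pressure, pulse, ECG | Visits 1–7, before open-label dosing | 7.01–10 |
| **Immunogenicity** | **Visit 3** | **3.01–10** |

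The blood pressure, pulse and ECG row, for example, sets "Last non-missing value from Visits 1–7 before open-label phase dosing for patients treated with placebo during SP III" as baseline and "Visits 7.01–10 for placebo-treated patients during SP III" as the window. Only the immunogenicity row has no split, and no reason is given.

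**3. Worked case under the Section 6.13 rule.** A placebo patient is ADA-negative at Visit 3, positive with titre 20 or more at Visit 5 or at pre-dose Visit 7, and then enters Study Period IV. The patient meets the treatment-induced definition within Visits 3.01 to 10. The patient is counted as emergent on galcanezumab even if nothing new appears after the first dose. The same holds for a 4-fold rise from Visit 3 that is already present at Visit 5 or 7.

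**4. Illustration of size.** The inputs from the documents are 243 patients per arm and 20% discontinuation in the double-blind phase (protocol Section 10.1; SAP Section 5.2). The placebo-period rate of treatment-emergent ADA and the uptake of the open-label phase are assumptions.

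- Switchers if every placebo completer opts in: 243 × 0.8 ≈ 194. Population: 243 + 194 = 437.
- Switchers if half opt in: 97. Population: 243 + 97 = 340.
- Misattributed patients = rate × switchers. Added points = 100 × misattributed ÷ population.

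| Assumed placebo rate | 194 switchers: patients, points | 97 switchers: patients, points |
|---|---|---|
| 1% | 1.9, +0.4 | 1.0, +0.3 |
| 3% | 5.8, +1.3 | 2.9, +0.9 |
| 5% | 9.7, +2.2 | 4.9, +1.4 |

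These counts treat every placebo-period positive as extra. Suppose instead that 5% of all patients, independently, become emergent on galcanezumab. The pooled rate is then 5% + rate × 0.95 × switchers ÷ population. With 194 switchers it reads 5.4% at a 1% placebo rate and 7.1% at a 5% placebo rate, against a true 5%. With 97 switchers it reads 5.3% and 6.4%.

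**The case against.** Five points can be made for the plan as it stands.

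- **The block heading could limit the window.** A programmer might read 3.01–10 as an outer range, cut down for switchers by the definition of galcanezumab-treated time. This is the weaker reading. The cell explicitly includes all visits in the range, Section 6.13 defers to the table, and the neighbouring rows state the split outright.
- **The combined row may hold no switchers.** It does not use the defined population name, and elsewhere in the table similar wording means the original galcanezumab arm. The ambiguity is real. However, Section 6.13 uses the same description of patients for both summaries, and a split does no harm if the row contains no switchers.
- **The reach is limited.** This stands. The only between-group ADA comparison planned, in Study Period III with Visit 3 as baseline and Visits 3.01–7 as window, is sound. The affected outputs are descriptive, and no efficacy test is touched.
- **The size rests on assumed rates, and the error can go either way.** This stands. Full uptake of an optional phase is an upper bound. Some placebo-period positives would also qualify after galcanezumab. A switcher positive at Visit 3, negative at Visit 7 and back at the Visit 3 titre at Visit 10 is missed under the current rule.
- **The split leaves unequal follow-up.** This also stands. In galcanezumab-treated time, switchers would have one scheduled post-baseline sample (Visit 10), against three for the original arm. That is a reason to show the two groups separately, not to count placebo samples.

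**Conclusion.** The concern holds: the rule is wrong as written. It gives switchers a window that contradicts the SAP's own start of galcanezumab-treated time, and nothing in Section 6.13 corrects it. With 97 to 194 switchers and an assumed placebo-period rate of 1% to 5%, about 1 to 10 patients would be misattributed, adding at most about 0.3 to 2.2 percentage points to the pooled incidence. Those rates and the uptake are not in the documents, and the upper figures assume that every placebo completer switches and that no misattributed patient would have qualified anyway. The correction should be made, but it does not bear on the trial's primary or key secondary conclusions.

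**What to change.** Change the two immunogenicity rows of SAP Table CGAX.6.1 (galcanezumab-treated time, and Study Periods III/IV/V combined).

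- **Placebo in Study Period III:** baseline is the last sample before the first galcanezumab dose, meaning pre-dose Visit 7 or, if missing, the last earlier sample. The post-baseline window is Visits 7.01–10 for galcanezumab-treated time and 7.01–12 for the combined row.
- **Randomized to galcanezumab:** keep Visit 3 as baseline and 3.01 onward as the window.
- **Combined row:** state whether it includes switchers.
- **Presentation:** show the incidence by original arm beside the pooled figure, because the number of post-baseline samples differs.

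The cost is an edit to two table rows and a small programming change. The Visit 7 sample is already scheduled. Section 6.1 allows SAP changes only before unblinding; if that point has passed, the change and its reason can be described in the clinical study report.
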